### **Analysis of Primary and Secondary Outcomes:**

The primary endpoint of the study is the percentage change of normalized degradation at 24h post-surgery. Primary comparison will be the difference of the primary endpoint between neonates randomized to Cyro and those randomized to FC, with the primary focus on 24h post-surgery time point. To answer this primary research question, we will utilize two sample t-test or Wilcoxon rank sum tests to compare percent change from pre-surgery (baseline) between groups at 24h post-surgery. We will further employ linear mixed models to analyze the longitudinal endpoints accounting for repeated measures. Specifically, we will examine percentage change of normalized degradation at follow up time points (i.e., post-surgery, ICU admission, and 24h post-surgery) relative to baseline between the two groups. Random intercepts at patient level will be included to account for within-subject correlation. Post-hoc comparison between time points will be conducted by contrasts. Results will be presented as difference in least square means between groups or between time points, with associated 95% confidence intervals. Analysis of secondary outcomes, including measurements collected post-transfusion, will be analyzed using similar methods.

Finally, two sample t-tests or Wilcoxon rank sum tests will be used to examine the difference in clot kinetics (i.e., structure, polymerization, degradation) and clinical outcomes including chest tube output, 24-transfusion needs, and ICU length of stay. Two-sample t-tests or Wilcoxon rank sum tests will be used to compare measures between patients with and without thrombotic events. Multivariable linear regression for continuous outcomes and logistic regression for binary outcomes will be used to examine the association between the clot kinetics and clinical outcome while adjusting for potential confounders including pre-surgical weight, age, cardiac diagnosis/ RACHS score, and pre-operative comorbid conditions, as needed.

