## **Sample Size Considerations**

The primary endpoint of the study, on which the statistical power is based, is the difference in clot degradation time at 24 hours post-operatively in neonates randomized to Cyro compared to those randomized to FC, with the primary focus on the overall set of subjects in the ITT population. Based on our previous work comparing adult and neonates, we observed a large difference (>2 standard deviation (SD) difference) in degradation times between the adults and neonates. In this study, we conservatively estimate a 1 SD difference in mean degradation times when comparing degradation times between infants randomized to Cyro vs. those randomized to FC. Assuming a two-sided test at the 5% significance level, 17 completed participants will provide 80% power to detect a 1 SD difference in mean degradation times between our two groups at 24-hours post-operative. Power was calculated using a two-sample t-test. Additionally, assuming an attrition of 1 per group (i.e., death before 24 hour endpoint), 18 participants are// needed for enrollment into the study to ensure an adequate number of subjects complete the primary endpoint. Power calculations were made using PASS v. 14.0.8 (Kaysville, UT).

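### The primary test uses unadjusted percent change from baseline, while the 80% power was computed for the 24-hour value; adjusting for the baseline already measured costs nothing and guards against a possible loss of power.

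*SAP*

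**What the plan says.** The SAP describes the primary endpoint in two ways. Under Sample Size Considerations it is the "difference in clot degradation time at 24 hours post-operatively in neonates randomized to Cyro compared to those randomized to FC". The effect and test there are: "we conservatively estimate a 1 SD difference in mean degradation times" and "Power was calculated using a two-sample t-test". The result is that "17 completed participants will provide 80% power to detect a 1 SD difference in mean degradation times between our two groups at 24-hours post-operative". This means 17 per arm, because the protocol enrols 36 infants, 18 per arm, and the SAP allows one loss per group.

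Under Analysis of Primary and Secondary Outcomes the endpoint is different: "The primary endpoint of the study is the percentage change of normalized degradation at 24h post-surgery". For the test, "we will utilize two sample t-test or Wilcoxon rank sum tests to compare percent change from pre-surgery (baseline) between groups at 24h post-surgery". The mixed model that follows also takes percent change as its outcome and names no baseline covariate. The adjustment list in that section (weight, age, diagnosis or RACHS score, comorbid conditions) belongs to the models that link clot kinetics to clinical outcomes. The protocol's statistical section names no covariate either.

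General Statistical Considerations sets out normality checks. It ties them to how data are presented and does not make them a rule for choosing between the t-test and the Wilcoxon test.

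**The concern.** Percent change divides each infant's 24-hour value by that infant's own baseline. This helps when the two values are strongly correlated. When they are not, the division brings baseline variability into the endpoint without removing much in return. Between the two samples each infant has bypass, plasma in the circuit, platelets and an adult fibrinogen product, so a weak correlation is plausible, though the documents report none.

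The sample size has almost no slack. If the quantity tested is noisier than the quantity powered, the 80% no longer describes the test that will be run. A regression with baseline as a covariate estimates how much of the baseline to subtract, and the protocol already schedules a baseline sample for every infant.

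**Working it through.** **Inputs from the SAP:** two-sided 5% level, 17 completers per arm, 1 SD difference in 24-hour degradation time, two-sample t-test.

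**Inputs assumed, because the documents do not give them:** the baseline-to-24-hour correlation ρ, taken from 0 to 0.7, and k = baseline CV / 24-hour CV, taken from 0.5 to 2.

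**1. The plan's own figure.** Noncentral t power with standardized difference d = 1 is 80.7% at 17 per arm and 78.1% at 16. The stated 17 and 80% are reproduced.

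**2. Standardized difference under each analysis**, with a true effect of 1 SD on the 24-hour scale:
- Percent change, by the delta method: d = 1/√(1 + k² − 2ρk). With equal CVs (k = 1) this is 1/√(2(1 − ρ)), the usual change-score formula.
- Regression on arm and baseline: d = 1/√(1 − ρ²), with 2 × 17 − 3 = 31 degrees of freedom.

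For example, at ρ = 0.3 and k = 1, percent change has d = 1/√1.4 = 0.845, and regression has d = 1/√0.91 = 1.048.

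**3. Power at 17 per arm, equal CVs (k = 1):**

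| ρ | Percent change | Baseline-adjusted |
|---|---|---|
| 0 | 51.6% | 80.6% |
| 0.3 | 66.6% | 84.1% |
| 0.5 | 80.7% | 90.3% |
| 0.7 | 95.4% | 97.7% |

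For 80% power, percent change would need 33 per arm at ρ = 0 and 23 at ρ = 0.3. Adjustment needs 17 and 16.

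**4. Correlation that percent change needs for 80%, by CV ratio:**

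| k | 0.5 | 0.75 | 1 | 1.25 | 1.5 | 2 |
|---|---|---|---|---|---|---|
| ρ needed | 0.23 | 0.36 | 0.49 | 0.62 | 0.74 | about 0.99 |

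At k = 0.5 the gap is small: 71.5% v 80.6% at ρ = 0, 82.6% v 84.1% at 0.3, and 90.4% v 90.3% at 0.5.

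**5. Why adjustment is not the worse choice.** The two variance factors differ by (1 + k² − 2ρk) − (1 − ρ²) = (k − ρ)², which is never negative. They tie only at k = ρ, where adjustment loses about 0.1 point for its one degree of freedom. These formulas leave out chance baseline imbalance between the arms. Simulation includes it and puts adjusted power at ρ = 0 at 79% to 80% rather than 80.6%, so near the tie adjustment could trail by up to about a point.

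**6. Simulation check.** Lognormal values with equal CVs of 30% to 50%, 4,000 trials per cell:

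| ρ | t-test on percent change | Wilcoxon on percent change | Log-scale adjustment |
|---|---|---|---|
| 0 | 43–49% | 49–50% | 79–80% |
| 0.3 | 60–64% | 63–65% | 82–83% |
| 0.5 | 77–80% | 78% | 89–90% |
| 0.7 | 94–95% | 94–95% | 97% |

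The Wilcoxon option does not close the gap.

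**The case against.** A reader might infer that the trial falls short of 80% unless the correlation reaches about 0.5, or that a third of the power is lost. Neither is established. The 0.5 requires equal CVs at baseline and 24 hours, and the large loss also requires zero correlation. With a baseline CV half the 24-hour CV, the requirement drops to about 0.23 and the loss is modest or nil. With a ratio above 1 it is worse. The documents fix neither the ratio nor the correlation.

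The calculation also places the 1 SD on the 24-hour scale. The sample-size section words it that way, but the analysis section names a different endpoint. If the 1 SD was meant for percent change, power is 80.7% at any correlation.

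Nor does the problem arise whichever degradation variable is primary. If the 24-hour time governs and is compared directly, no baseline enters, the stated power is right, and adjustment only adds to it. It would also be too strong to say that percent change adds all of the baseline noise. That is so only at zero correlation, since any positive correlation offsets part of it.

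Two smaller points stand. The lognormal simulation suits a log-scale model, although the formulas, which do not assume lognormal values, give the same ordering. And the SAP does not define normalized degradation, so its fitness for a log model is unverified.

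These objections limit the size of the claim. They do not touch the facts that the powered and tested quantities differ and that no stated model adjusts for baseline.

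**Conclusion.** The point holds as a mismatch with a free remedy. The 80% applies to the unadjusted 24-hour value, and the SAP tests unadjusted percent change. With the 1 SD on the 24-hour scale and equal CVs, percent change has about 52%, 67% and 81% power at correlations 0, 0.3 and 0.5, against 81%, 84% and 90% with adjustment. The actual shortfall, if any, cannot be determined from the documents.

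The recommendation does not depend on those unknowns. For a linear relation between baseline and 24-hour values in randomized arms, adjustment matches or beats percent change over the whole assumed range, to within the small margin in step 5. This is a change the sponsor should make, and not a demonstration that the trial is underpowered.

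**What to change.** In Analysis of Primary and Secondary Outcomes, name one primary analysis in the intention-to-treat set: a regression of 24-hour degradation on arm and baseline degradation.
- If the normalized variable is strictly positive, take logs of both values and report the FC/cryoprecipitate ratio of geometric means with its 95% confidence interval and two-sided p-value. Otherwise use the raw scale and report the adjusted mean difference.
- Keep percent change as a descriptive summary.
- Make a rank-based version of the same model the sensitivity analysis. This also settles the open choice between two tests.
- Use the same model for the secondary clot measures.

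In Sample Size Considerations, say that the 80% refers to the 24-hour value, and give the assumed SDs and correlation if earlier data supply them.

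The cost is one SAP paragraph and a clarifying sentence, one degree of freedom, and, on the log scale, a result reported as a ratio. No infant, sample or visit is added.

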Arvada, CO, USA). All circuits contain a 250-300 ml priming volume, which include 50ml 25% albumin (Grifols), Plasmalyte, 0.5mg/kg mannitol, calcium gluconate, and 8.4% sodium bicarbonate to normalize the pH. Packed RBCs (pRBCs) are added to the circuit as needed to achieve and maintain a hematocrit of 30% throughout the duration of CPB. In accordance with institutional policy, patients having cardiac surgery receive pRBCs that are less than 14 days old. 50ml fresh frozen plasma (FFP) is added to CPB prime and another 50 ml FFP is added upon re-warming. Conventional or zero-balance ultrafiltration is performed throughout the bypass period at both institutions. For all patients, pH-stat blood gas management is used during bypass.

Anticoagulation

Anticoagulation is established with 500units/kg of porcine heparin with 1000 units of heparin added to the CPB prime. Kaolin-activated ACT values greater than 480 seconds are confirmed prior to the initiation of CPB (i-STAT®1 Analyzer; Abbot Point of Care Inc, Abbott Park, IL, USA). Additional heparin is administered as necessary during CPB to maintain an ACT >480 seconds. After completion of surgery, patients are rewarmed to 36°C and weaned from CPB. Protamine (5mg/kg) is used to neutralize heparin upon completion of CPB and confirmed with ACT. Additional protamine is administered if ACT levels are above baseline values. All neonates (patients <30 days of age) will receive anti-fibrinolytic therapy. Tranexamic acid was used: 100mg/kg bolus dose pre-bypass, 100mg/kg bypass dose, and an infusion at 10mg/kg/hr that was terminated at transport to the ICU.

Transfusion Algorithm: In order to minimize confounding factors, a transfusion algorithm and transfusion thresholds will be followed in the operating room and ICU for all patients enrolled in the study. RBCs will be transfused for hematocrit <32% for acyanotic neonates, while cyanotic neonates are transfused RBCs for a goal Hct 35-40%. RBC transfusion is not permitted for hematocrit values higher than 45%.

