Aim 2 (Correlation of clot properties to clinical outcomes): Clinical outcome variables will be collected for each patient and correlated to clot properties with specific attention to: 1) transfusions within the first 24 hours of surgery, 2) 24-hour chest tube output, 3) clinical signs and symptoms of postoperative thrombosis. Our multi-site prospective, randomized control trial demonstrated that FC can reduce allogenic blood transfusion in neonates and infants undergoing elective cardiac surgery with CPB when compared to cryoprecipitate. Our proposed laboratory studies use platelet poor plasma to enable us to focus on the contribution of supplemental fibrinogen to neonatal clot kinetics. However, since platelets, particularly the increased dependence on vWF in neonates, also play an important role in post-bypass hemostasis, we plan to correlate clinical characteristics and outcomes with our findings regarding clot kinetics. Clinical outcome variables will be collected for each patient and correlated to clot properties with specific attention to 1) transfusion requirements intraoperatively; 2) transfusion requirements within the first 24 hours of surgery; 3) post-operative bleeding recorded by 24 hour chest tube output; 4) clinical signs and symptoms indicative of postoperative thrombosis; 5) mechanical ventilation time; 6) length of ICU and hospital stay 7) adverse events within seven days of surgery. While our study is not powered to for this outcome, we hope that these data will provide some insight in to the clinical differences between different sources of adult fibrinogen.

Samples Size/Statistical Analysis

Data collected will include demographic data, CBP data, transfusion data, laboratory data and clinical outcomes listed above. As we demonstrated in prior work, neonatal clots prior to transfusion displayed a significantly higher degree of alignment when compared to those composed of adult only or mixed neonatal and adult fibrinogen. Based on our previous data, to detect a difference in degradation times between clots formed with neonatal fibrinogen and clots formed with adult fibrinogen with 80% power, we will enroll a total of 36 patients, with 18 in patients in each arm. All quantitative data will be analyzed using a paired t-test or Wilcoxon rank-sum test to

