## **General Statistical Considerations**

Descriptive statistics will be calculated for all variables of interest. For continuous variables this will include means and standard deviations, medians, quartiles (25th, 75th), minimum and maximum values. Categorical data will be described using counts and percentages. Continuous data will be assessed for normality using histograms and normal probability plots and statistically tested using the Anderson-Darling test and/or the Shapiro Wilk test for normality. Non-normal data will be presented using medians accompanied by 25th and 75th percentiles.

No adjustments will be made for testing multiple secondary and exploratory efficacy outcomes. Given the large number of secondary/exploratory outcomes, the p-values associated with such outcomes will be considered descriptive as the likelihood of making a type I error is inflated due to multiple testing. All analyses will be conducted using SAS v. 9.4 (Cary, NC) or CRAN R v. 3.3 or above (Vienna, Austria). All statistical testing will be two-sided and performed using a 0.05 significance level (i.e., alpha =0.05). Missing values at baseline will be imputed using group median values at the specific time points. We will also repeat all analyses without imputation as a sensitivity analysis.

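### The SAP's supporting longitudinal model names only a patient random intercept, so its 24-hour interval rests on a variance averaged over three times and is wrong if spread at 24 hours differs

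*SAP*

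**What the plan says.** The SAP section on primary and secondary outcomes answers the primary question with a two-sample t-test or Wilcoxon rank sum test on percent change from baseline at 24 hours. It then adds a linear mixed model over three follow-up times: post-surgery, ICU admission and 24 hours. On covariance it says "Random intercepts at patient level will be included to account for within-subject correlation". It states no residual structure, time-specific variance, robust standard error, degrees-of-freedom method or list of fixed effects.

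On reporting, it says "Results will be presented as difference in least square means between groups or between time points, with associated 95% confidence intervals". This is the only place where the SAP names an interval for a difference between arms.

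Sample Size Considerations bases power on the single 24-hour time: "Assuming a two-sided test at the 5% significance level, 17 completed participants will provide 80% power to detect a 1 SD difference" and "Power was calculated using a two-sample t-test". The Protocol's Anticoagulation section describes an antifibrinolytic given as boluses and as "an infusion at 10mg/kg/hr that was terminated at transport to the ICU". The post-transfusion sample therefore falls in the operating-room phase of that infusion, the ICU-arrival sample follows soon after it, and the last sample is taken a day after surgery.

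**The concern.** A random intercept with independent, equal-variance residuals is compound symmetry: one variance at all three times and one correlation for every pair. Two of the samples are perioperative and close together, and the third comes a day later under different conditions. Nothing in either document supports equal spread or equal correlation across them.

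If spread differs, the model's 24-hour standard error borrows from the wrong times. The interval is too narrow when 24-hour spread is the larger and too wide when it is the smaller. It can then contradict the t-test run on the same 24-hour data. If correlations differ, the contrasts between time points that the SAP also promises are miscalibrated, even with equal SDs.

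**Working it through.** **Inputs from the documents.** Two-sided alpha 0.05, a 1 SD difference and 17 completers (SAP, General Statistical Considerations and Sample Size Considerations); 18 per arm, 36 in total (Protocol, sample size section: "we will enroll a total of 36 patients, with 18 in patients in each arm"); three follow-up times (SAP, outcomes section).

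**Assumed, because no document gives them.** The ratio k of the 24-hour SD to the SD at the two earlier times; within-infant correlation 0.5; independent equal-variance residuals; and a group-by-time term, so that the model has a 24-hour contrast at all.

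**1. The plan's own figure.** For a two-sample t-test with 17 per arm, df = 32 and noncentrality = 1 × √(17/2) = 2.92. Power is 80.7%; 16 per arm gives 78.1%. The SAP's 80% reproduces if 17 is read as per arm. Read as a total (8 or 9 per arm), power would be only 46% to 51%. Adding one loss per arm gives 18 and 36. With 18 complete per arm, power is 83%.

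**2. The variance that the model uses at 24 hours.** Let Σ be the true 3×3 covariance within an infant and S the sum of all its entries. In balanced data the random-intercept variance at any one time is (MSB + 2·MSE)/3, where

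- E(MSB) = S/3
- E(MSE) = (trace Σ − S/3)/2

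The sum MSB + 2·MSE has expectation trace Σ, so the variance used is trace Σ/3, the plain mean of the three variances. The correlations cancel, which is why the results barely move between correlations 0.3, 0.5 and 0.7.

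With the 24-hour SD set to 1 and the earlier SDs to 1/k, the variance used divided by the true variance is (2/k² + 1)/3. The standard error is multiplied by the square root of that.

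**3. Consequences for the mixed-model 24-hour contrast** (simulated trials, 18 per arm, complete data, Satterthwaite df):

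| k | SE multiplier | Result, against 5% type I error and 83% power |
|---|---|---|
| 0.5 | √3.000 = 1.73 | power at 1 SD about 34% |
| 0.67 | √1.818 = 1.35 | power about 62% |
| 0.8 | √1.375 = 1.17 | power about 75% |
| 0.9 | √1.156 = 1.08 | power about 80% |
| 1 | 1.00 | no error |
| 1.1 | √0.884 = 0.94 | type I error about 6.5% |
| 1.25 | √0.760 = 0.87 | type I error about 9% |
| 1.5 | √0.630 = 0.79 | type I error about 12% |
| 2 | √0.500 = 0.71 | type I error about 16% |

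A variance specific to 24 hours stays near 5% and 83% in every row. At the planned 17 completers per arm the power benchmark is about 81%. The model's 95% CI then covers about 91%, 88% and 84% at k = 1.25, 1.5 and 2, and 99.9% at k = 0.5.

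**4. Cross-check with fitted mixed models** (17 per arm). Mean fitted standard errors at k = 0.5, 1 and 2 were 0.593, 0.345 and 0.238. The averaging formula gives 0.594, 0.343 and 0.243. The true value is √(2/17) = 0.343 throughout.

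**5. Disagreement with the t-test.** At a true 1 SD effect with 18 per arm, the model and the t-test reach different verdicts at 24 hours in about 21% of trials at k = 0.67 and 9% at k = 1.5, against 3% at k = 1.

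**6. Contrasts between times.** Assume equal SDs of 1, correlation 0.8 between the first two samples and 0.3 between each of them and 24 hours. The model's common correlation is (0.8 + 0.3 + 0.3)/3 = 0.47, so it gives every change a variance of about 2 × (1 − 0.47) = 1.06. The true values are 2 × (1 − 0.8) = 0.40 for the first-to-second change and 2 × (1 − 0.3) = 1.40 for a change to 24 hours. Simulated error rates are about 0.2% and 9%.

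**The case against.** The strongest reply is that the primary analysis does not use this model. The SAP answers its primary question, and sizes the trial, with a two-sample comparison at 24 hours; the mixed model comes afterwards. A reader might take the 16% or the 34% as the trial's primary error rate or power. The documents do not support that: these figures describe a supporting contrast.

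Three other inferences also go too far.

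- A reader might say that the SAP chose a random intercept and nothing else. It says that random intercepts will be included and is silent on the residuals; compound symmetry is the ordinary default reading of that silence.
- A reader might say that the headline 24-hour interval must come from this model. No sentence says so, and nothing bars an interval from the t-test.
- A reader might treat the antifibrinolytic as proof of unequal spread. It shows that sampling conditions differ; no document links it to the variability of the endpoint, and even the direction of any difference is unknown.

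It can also be said that the unstructured model repeats an analysis already planned, since with complete data its 24-hour contrast equals the pooled t-test. That is true at 24 hours, but it also shows that the richer structure gives up almost nothing. If the Wilcoxon test is used instead, no covariance choice guarantees agreement with it.

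What stands is that the one arm-difference interval named in the SAP follows from a model whose equal-variance assumption is neither stated nor supported, and that the between-time contrasts depend on the same assumption.

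**Conclusion.** The point holds for the supporting longitudinal model and its least-square-mean intervals. It does not touch the primary 24-hour p-value.

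Its size depends wholly on an SD ratio that the documents do not give. It is nil at equal spread and small for departures of about 10%. It is material at 1.5 times (type I error about 12%) or 0.67 times (power about 62% instead of 83%). These figures rest on 18 complete infants per arm, correlation 0.5, a fitted group-by-time term and the default residual structure. The change is worth making because it is cheap and brings the reported interval into line with the test on which the trial was sized.

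**What to change.** In the SAP section on primary and secondary outcomes, replace the random-intercept sentence with a full specification:

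- fixed effects for group, time and group-by-time;
- an unstructured within-infant covariance over the three follow-up times;
- Kenward-Roger degrees of freedom;
- heterogeneous compound symmetry as the fallback if the model does not converge.

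Add that the 24-hour arm difference and its 95% CI come from this model or, equivalently with complete data, from the primary two-sample t comparison.

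The cost is a few lines of SAP text and code, with no change to sample size or sampling. Three times need six covariance parameters (three variances, three correlations) against two now, so four more. If spread really is equal, the loss is about one point of power. There is a small chance of needing the fallback.

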Randomization As they present to Children's Healthcare of Atlanta, patients will be enrolled consecutively and randomized to receive either FC or cryoprecipitate as part of a standardized transfusion algorithm. Once on CPB, patients will be randomized using block randomization with variable blocks. Patients will be randomly assigned (1:1) to receive either cryoprecipitate (control group) or fibrinogen concentrate (FC) (study group) as part of our post-bypass transfusion algorithm. Ideally, all practitioners would be blinded to the study. However, the dose of fibrinogen concentrate is diluted in normal saline and may be up to approximately 50mls. The use of a placebo would require the administration of up to 50mls of normal saline, 20% of a blood volume in a 3kg neonate. The hemodilutional effects of placebo would potentially confound the results comparing the two groups. Therefore, the anesthesiologist, who will be administering either cryoprecipitate or FC, will be aware of the group allocation. Parents, surgeons, and critical care physicians will be blinded to the group allocation.

Rationale for Standardized Anesthetic, Cardiopulmonary Bypass and Anticoagulation Management In order to minimize confounding factors, we will follow our standard anesthetic management, cardiopulmonary bypass protocol, and anticoagulation strategy.

Anesthesia Management and Cardiopulmonary Bypass Management

Anesthesia, CPB, and surgery will be performed by the same teams of anesthesiologists, perfusionists, and surgeons. Anesthesia techniques will follow institutional protocol, which include a balanced anesthesia technique and necessary invasive monitoring, including arterial and central pressure monitoring.

Cardiopulmonary Bypass management

Nonpulsatile CPB is performed using a nonheparin-coated system, a Terumo FX-05 hollow-fiber membrane oxygenator (Terumo Cardiovascular Systems, Ann Arbor, MI), and Livanova SMArt-coated neonatal circuit (LIVANOVA USA (Sorin Group USA),

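### The SAP has no rule for how an infant's death enters the comparison of ICU length of stay; taken at face value, an early death counts as one of the shortest, most favourable stays.

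*SAP*

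**What the plan says.** The relevant statements lie in several places.

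- **Outcomes and test.** SAP, Analysis of Primary and Secondary Outcomes: "two sample t-tests or Wilcoxon rank sum tests will be used to examine the difference in clot kinetics" and in "clinical outcomes including chest tube output, 24-transfusion needs, and ICU length of stay". I read this as a comparison of the two randomized arms.
- **Further duration outcomes.** Protocol, Aim 2 (Correlation of clot properties to clinical outcomes), also lists "5) mechanical ventilation time; 6) length of ICU and hospital stay". There they are variables to be correlated with clot properties. The SAP sentence names neither ventilation time nor hospital stay.
- **Who is analysed.** SAP, Study Populations: the ITT set is everyone enrolled, by randomized assignment, and is the primary analysis.
- **Expected deaths.** SAP, Sample Size Considerations: "assuming an attrition of 1 per group (i.e., death before 24 hour endpoint".
- **Missing data.** SAP, General Statistical Considerations: the only imputation rule concerns baseline values. The same section calls p-values for secondary and exploratory outcomes descriptive.
- **Death as a safety event.** Protocol, Data Safety Monitoring Plan: deaths go to the DSMB within 24 hours. Nothing links them to the outcome analyses.

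**The concern.** Length of stay can end in two opposite ways, discharge or death, and a plain two-group test on days does not tell them apart. The SAP anticipates deaths on the first day, keeps those infants in the analysis set and gives no scoring rule, so the handling will be settled after the data are seen.

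Neither of the two default choices is satisfactory. Using the days actually spent in the ICU turns a death into a very short stay. Excluding the infant abandons the ITT comparison and conditions on surviving, which is itself an outcome after randomization.

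What is at stake is the descriptive clinical comparison of fibrinogen concentrate (FC) with cryoprecipitate. Under the first choice, the arm with more early deaths is credited with shorter stays, an error in the unsafe direction.

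**Working it through.** **1. The plan's own figure.** Inputs: "Assuming a two-sided test at the 5% significance level, 17 completed participants will provide 80% power to detect a 1 SD difference", and "Power was calculated using a two-sample t-test". With the noncentral t distribution, two-sided 5%, 1:1 and a 1 SD difference, 16 per arm gives 78.1% power and 17 per arm gives 80.7%. Adding one death per arm gives 18 per arm, or 36 in all. This agrees with the protocol ("we will enroll a total of 36 patients"; "Patients will be randomly assigned (1:1) to receive either cryoprecipitate"). The design reproduces, and the expected early-death rate is 1/18 = 5.6% per arm.

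**2. Where an early death ranks on ICU stay.** An infant who dies before 24 hours has a stay under 1 day. The documents give no distribution of stay, so I assume lognormal stays in survivors. The share of survivors with a stay under 1 day is Φ(−ln(median)/log-SD):

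| Assumed median (days) | log-SD 0.5 | log-SD 0.7 | log-SD 0.9 |
|---|---|---|---|
| 4 | 0.3% | 2.4% | 6.2% |
| 7 | 0.0% | 0.3% | 1.5% |
| 14 | 0.0% | 0.0% | 0.2% |

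Scored at face value, the death therefore ranks at or near the shortest stay.

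**3. Effect on the between-arm comparison.** Suppose k deaths in one arm of 18, none in the other, and identical stays among survivors. The probability that a random infant from the arm with deaths has the shorter stay is:

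- at face value, (k + (18 − k)/2)/18
- deaths excluded, 1/2
- death ranked worst, ((18 − k)/2)/18

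| k | Face value | Excluded | Worst rank |
|---|---|---|---|
| 1 | 9.5/18 = 0.53 | 0.50 | 8.5/18 = 0.47 |
| 2 | 10/18 = 0.56 | 0.50 | 8/18 = 0.44 |
| 3 | 10.5/18 = 0.58 | 0.50 | 7.5/18 = 0.42 |

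Simulation with survivor median 7 days and log-SD 0.7 agrees (0.554 at face value and 0.443 at worst rank for k = 2). With one death in each arm all three methods give 0.50.

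**4. Nominal significance at face value.** The rank-sum U has SD √(18 × 18 × 37/12) = 31.6, so the one-sided 2.5% cut-off lies 1.96 × 31.6 = 61.9 from its centre. Each death ranked shortest moves U by 9. The rest of U has SD √((18 − k) × 18 × (37 − k)/12).

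- k = 1: (61.9 − 9)/30.3 = 1.75, giving 4.0%
- k = 2: (61.9 − 18)/29.0 = 1.52, giving 6.5%
- k = 3: (61.9 − 27)/27.7 = 1.26, giving 10.3%

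Simulations under the step 3 assumptions, with deaths at 0.5 day, gave 3.6% to 4.1%, 6.4% to 6.7% and 10.3% to 10.8%. A t-test on the same data gave 3.4%, 5.7% and 7.7%, so the problem does not depend on which of the two tests is used.

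**5. The 24-hour totals.** Here the direction is not fixed. Assume survivors' chest tube output is lognormal with log-SD 0.6, and that the infant bleeds at m times the typical rate until death at hour t. Relative output is m × t/24, and its percentile among survivors is Φ(ln(m × t/24)/0.6):

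- t = 6, m = 1: relative output 0.25, about the 1st percentile
- t = 6, m = 4: 1.0, the 50th percentile
- t = 12, m = 4: 2.0, the 88th percentile

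The total is cut short, but it can look good or bad. The same reasoning applies to transfusion within 24 hours.

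**The case against.** Several points on the other side stand.

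- **Scoring at face value is an inference from silence.** The SAP calls these deaths attrition and counts completers, so exclusion is an equally natural reading. Under exclusion, with equal survivors, the comparison sits at 0.50 in every scenario. That removes the favourable score for death but leaves a survivor-only comparison inside an analysis labelled ITT. The gap remains on either reading.
- **The planned case is balanced.** With one death per arm the between-arm bias roughly cancels. The 2 versus 0 and 3 versus 0 cases are illustrations, not expectations in the documents. With 18 per arm, though, unequal deaths can arise by chance.
- **The outcomes carry limited weight.** The protocol says the study is not powered for the clinical outcomes, and the SAP treats the p-values as descriptive. Deaths also reach the DSMB, so an excess would not be hidden. A descriptive difference in stay is still biased in the same way.

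A reader might infer that an early death also produces falsely low chest tube output and transfusion. Step 5 shows that this does not follow, and the protocol's introduction itself associates greater transfusion with mortality. A reader might also infer that ventilation time is compared between arms; the SAP does not name it. Finally, one might expect early deaths to distort the regressions on 24-hour clot kinetics. An infant who dies before 24 hours has no 24-hour sample, so only regressions on earlier samples could be affected.

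**Conclusion.** The point holds for ICU length of stay, and for ventilation time and hospital stay if they are analysed. The plan expects early deaths, retains those infants, uses a plain two-group test and gives no rule for death. Taken at face value, such a death is one of the most favourable stays in the dataset.

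The size depends on the imbalance in deaths. It is about nil at one per arm. At two versus none, the arm with the deaths has about a 55% chance of the shorter stay and about 6.5% one-sided nominal significance against 2.5%. These figures assume equal stays among survivors and deaths shorter than nearly all of them; the median of 7 days and log-SD of 0.7 are illustrative.

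For the 24-hour totals the finding is only that they are truncated in an uncertain direction. The primary endpoint and the sample size are not affected.

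**What to change.** In SAP, Analysis of Primary and Secondary Outcomes:

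1. Analyse ICU stay, and ventilation time and hospital stay if they are analysed, by rank sum with death before discharge given the worst rank. Alternatively, use ICU-free, hospital-free or ventilator-free days to a fixed day, with death scored 0.
2. Report deaths by arm beside these outcomes.
3. For chest tube output and transfusion, state that the total of an infant who dies before 24 hours is not treated as a complete 24-hour value, and add a per-hour, per-kg sensitivity analysis. Worst-ranking death here is debatable, because it would turn a bleeding measure into a composite with death, so I do not ask for it.

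The cost is mainly SAP wording; enrolment stays at 18 per arm. The stay outcomes become composites with death, reported as ranks or free-days rather than mean days. Worst-ranking also pulls the result against the arm with more deaths (0.44 at two versus none), which is intended but should be stated. The free-days option needs stay and survival status to the chosen day. The protocol specifies adverse-event collection for seven days only, so that follow-up would have to be confirmed; the worst-rank option needs only status at discharge.
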